5.10 Human Subjects/Ethical Considerations

In the Prevention for Positives component of the study, a subset of patients enrolled at select HIV care sites in the two intervention communities will be randomized either to an intervention arm (receiving SOC prevention activities plus a computer-delivered intervention) or to the control arm (receiving only the SOC prevention activities at the care site). Individual-level data will be collected and analyzed. This component is a public health research requiring informed consent. Written informed consent will be obtained from participants.

The protocol and supporting study materials (the informed consent form and any advertising materials) will be submitted to appropriate IRBs (a central and/or local site IRBs) for ethical review prior to study initiation. Any subsequent modifications to these materials will be submitted to appropriate IRBs, and, at a minimum, they will be submitted annually for continuing review and approval by these same ethics boards.

Written informed consent will be obtained from each study participant (or a mark for those who are illiterate, which will be witnessed by a third party) prior to study enrollment. Each study site is responsible for developing an informed consent form for local use, based on the template provided with this protocol that describes the purpose of the study, the study procedures and the risks and benefits of participation, in accordance with all applicable regulations. Participants will be provided with a copy of their informed consent form if they wish to receive it.

A small incentive will be provided to study participants in the Prevention for Positives component to compensate them for transportation and time.

All study-related information will be stored securely at the study site in areas with access limited to study staff. To maintain participant confidentiality, a coded number will identify all study data and administrative forms. All local databases will be secured with password-protected access systems. Forms, lists, logbooks, appointment books and any other listings that link participant ID numbers to other identifying information will be stored in a separate area with limited access. A participant's study information will not be released without the written permission of the participant, except as necessary to: authorized medical care providers; monitors for the National Institute of Allergy and Infectious Diseases (NIAID) and/or its contractors; representatives of the HPTN Coordinating and Operations Center (CORE) and/or the (Statistics and Data Management Center) SDMC; other government and regulatory authorities; and/or the site IRB.

No study-specific laboratory testing will be conducted under this protocol. Therefore, no additional study-related test results will need to be reported to authorities. HIV care data collected during routine clinical care will be reported per local HIV and AIDS reporting requirements.

6.0 SURVEY OF PATIENTS AND PROVIDERS

6.1 Study Objectives for the Survey of Patients and Providers

The objectives of the survey of patients and providers study component are the following:

- To assess knowledge, attitudes and practices with regard to ART initiation, the potential of starting ART at higher CD4 cell counts, and the use of ART for prevention of HIV transmission
- To ascertain key socio-demographic and behavioral characteristics of study participants that cannot be obtained from routine HIV surveillance data
- To assess the acceptability and attitudes towards FIs

6.2 Design for the Survey of Patients and Providers

All participants in the Prevention for Positives component of the study will complete a patient survey module prior to and at the end of that study component. The survey will assess knowledge and attitudes regarding the use of ART in HIV disease and other key factors related to the feasibility and acceptability of the study's interventions.

Clinical providers who prescribe ART at HIV care sites in the intervention communities will be invited to complete a survey regarding their knowledge, attitudes and practices about the use of ART in HIV patients as well as FIs. Clinical providers will be surveyed

prior to and following the viral suppression intervention to assess trends in the provider knowledge, attitudes and practices.

6.3 Study Population for the Survey of Patients and Providers

The patient survey component of the study will include HIV-positive patients at select HIV care sites that are participating in the Prevention for Positives component of the study.

Prescribing clinical providers (*e.g.* physicians, nurse practitioners and/or physician assistants) at select HIV care sites in the Bronx and Washington, D.C. will participate in provider survey.

6.3.1 Inclusion Criteria

The inclusion criteria for the patient survey are identical to those for the Prevention for Positives component of the study.

Prescribing clinical providers (*e.g.* physician, nurse practitioner/nurse-midwife, or physician assistant) at select HIV care sites are eligible for the provider survey.

6.3.2 Exclusion Criteria

The exclusion criteria for the patient survey are identical to those for the Prevention for Positives component of the study.

There are no exclusion criteria for the provider survey.

6.4 Study Sites for the Survey of Patients and Providers

The patient survey will be conducted at those HIV care sites involved in the Prevention for Positives component. The provider survey will survey providers from participating HIV care sites in the Bronx, NY and Washington, D.C.

6.5 Study Procedures for the Survey of Patients

Once consented and enrolled in the Prevention for Positives component, the clinic study staff will train participants how to use the computer tablet. Randomization to intervention (SOC plus full CARE+/ACASI counseling session) or control arm (SOC alone) is done automatically within the software application following the user's login with an anonymous study ID. Up to 110 individuals will be assigned to each arm, per site. At the end of the first (baseline, month 0) session, both arms will be presented, via the computer tool, with a series of questions (the patient survey). This patient survey module will be repeated only one more time, at the end of the intervention (month 12).

6.6 Study Procedures for the Survey of Providers

Providers at participating HIV care sites in both cities will be recruited by an introductory letter followed by up to two e-mail reminders, then two phone calls by study staff, asking them to take the brief survey on a secure, anonymous website.

Providers who go to the Web site will read and click on a brief consent, then complete a short survey assessing attitudes and practices.

At the completion of the survey, a printable coupon, compensating them for their time will be generated.

6.7 Study Duration for the Survey of Patients and Providers

Participants in the patient survey will complete the survey upon enrollment in the Prevention for Positives study and at the end of that study component.

The provider survey will also take place twice, once at the time of initiation of the overall HPTN 065 study and at the end of the viral suppression component.

6.8 Statistics and Data Analysis for Surveys of Patients and Providers

Data for analysis of this study component will be derived from answers to survey questions provided by both the patients and providers. Patient surveys will be administered electronically, after the CARE+ intervention at the beginning and at the end of the intervention. All patient responses will be stored in an electronic and secure database. Limited personnel will have access to this database. Provider surveys will be administered over the Internet. The survey will be secure and responses will also be stored securely. Survey data will be provided to the Statistical Center for HIV/AIDS Research and Prevention (SCHARP) for the following analyses:

• To assess baseline knowledge, attitudes and practices regarding the use of ART and other key factors related to the feasibility and acceptability of the study interventions in the subset of survey participants in the Prevention for Positives study component

Descriptive statistics will be used to summarize the survey participants' attitudes regarding the use of ART and other key factors related to the feasibility and acceptability of the study interventions by site and combined.

• To compare the providers' knowledge, attitudes and practices about the use of ART, assessing these at study baseline and at study end at HIV care sites in the intervention communities

Descriptive statistics will be used to summarize the prescribing providers' knowledge, attitudes and practices about the use of ART, at study baseline and study end by site and combined. Chi-squared statistics will be used to compare the baseline data with study end data.

All Prevention for Positives data collected on the tablet computer will be password security-protected (anonymous study ID assigned timed to the millisecond of initial user log-in, with no way for patients to access other user's data). All study data will be accessible only to investigators, study staff and biostatisticians assisting with the analysis. The CARE+ Prevention application will reside on each tablet computer with encrypted data transferred to a secured server at each clinic. The session database will be backed up by study staff. The 12 HIV care sites will send their study data to a SCHARP server on a routine basis. Only authorized study staff members are able to log onto the tablet computers or to access the master study database.

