Linkage-to-Care: HIV test sites will be randomized to either the FI intervention or to the SOC for linkage of HIV-positive patients identified at the testing sites to HIV care sites. At HIV test sites assigned to FIs, HIV-positive patients will be provided with a coupon to redeem at participating HIV care sites in the community. Upon completion of HIV laboratory testing, patients with coupons will be given an FI (\$25 gift card) at an HIV care site. A \$100 gift card will be provided to patients upon completion of a care visit that includes interaction with a healthcare provider and discussion of HIV laboratory test results (*e.g.* CD4 cell count and viral load (VL) measurements).

Viral Suppression: HIV care sites will be randomized to either the FI intervention or the SOC for the achievement and maintenance of viral suppression. HIV care sites assigned to the FI intervention will provide an FI (\$70 gift card) to HIV-positive patients on antiretroviral therapy (ART) demonstrating a suppressed VL (as defined by <400 copies/mL) at quarterly care visits.

Prevention for Positives: In a subset of patients enrolled from select HIV care sites in the two intervention communities, patients will be randomized either to an intervention arm (receiving SOC prevention activities plus a computer-delivered intervention for sexual and behavioral risk reduction) or to the control arm (receiving only the SOC prevention activities at the care site). In the intervention arm a modified version of the computerized counseling platform called Computer Assessment and Risk Reduction Education for HIV-positives (CARE+) will be used with an Audio Computer Assisted Self-Interviewing technique (ACASI). The CARE+/ACASI intervention session will ascertain behavioral risk, assess self-efficacy/motivation, and provide tailored feedback on specific risk behaviors. The computer-delivered intervention session will also have CARE+/ACASI sessions every three months. However, participants in the control arm will only be administered behavior assessments via CARE+/ACASI and will not receive prevention messaging.

TLC-Plus: A Study to Evaluate the Feasibility of an Enhanced Test, Link to Care, Plus Treat Approach for HIV Prevention in the United States

SCHEMA (Continued)

Study Components (continued):

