Patient and Provider Surveys: The same computer system used for the Prevention for Positives intervention will be used to administer a survey to patients enrolled in that study component. The survey will assess their knowledge and attitudes towards ART use for treatment and prevention, ART adherence and FIs. Providers from these sites will be invited to complete a Web-based survey regarding their knowledge, attitudes and practices concerning ART for treatment and prevention as well as use of FIs. Both surveys will also collect some key sociodemographic data on surveyed populations to allow more in depth characterization of these populations.

Study Size: Each of the five study components has a target sample size.

- The universal offer of HIV testing will be made in EDs and during hospital admission at ~seven facilities in the Bronx, NY and ~seven in Washington, D.C. Additional focused messages promoting testing will be targeted to the entire population of each intervention community: the Bronx (population 1.4 million) and Washington, D.C. (population 600,000).
- The Linkage-to-Care component includes 40 HIV test sites (20 in each intervention community) and 40 HIV care sites (20 in each intervention community). We project that, by the end of the study, approximately 3000 new individuals in the two intervention communities will have tested positive for HIV.
- The Viral Suppression component includes the 40 HIV care sites (20 in each intervention community). Throughout the study duration, approximately 30,000 HIV-positive individuals will be in care, with an estimated 75% (22,500) eligible for ART in the two intervention communities.
- The Prevention for Positives component will be conducted at a total of twelve sites (six in each intervention community) with up to a total of 1320 patients participating.
- The patients at the twelve sites participating in the Prevention for Positives component will be surveyed. Providers at all participating HIV care sites will be invited to complete the provider survey.

HPTN 065 TLC-Plus: A Study to Evaluate the Feasibility of an Enhanced Test, Link to Care, Plus Treat Approach for HIV Prevention in the United States

OVERVIEW OF STUDY DESIGN AND RANDOMIZATION SCHEME

Summary of Study Components

Study Component	Design	Outcomes
Expanded HIV Testing	Descriptive, ecologic study	Feasibility
Linkage-to-Care	Two-arm, site-randomized, prospective, effectiveness study	Feasibility and effectiveness

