5.5 Intervention for Prevention for Positives

A modified version of CARE+ for HIV-positives will be used with Audio Computer Assisted Self-Interviewing (ACASI) to measure behavioral risk and to compare a full computer counseling intervention (assesses self-efficacy and motivation, provides tailored feedback on specific risk behaviors, shows skill-building videos, and helps the user make a risk-reduction plan) to a control session consisting only of ACASI ascertainment of risk behavior.

An additional component will be the utilization of the computer-based system described above to measure factors that impact both the acceptability of the interventions utilized in this study and the feasibility of future TNT strategies. Other data, beyond those that can be obtained from routine HIV surveillance data, will be captured including the following:

• HIV testing history and prior experience with linkage/drop out from care (if applicable)

- CD4 cell count (via chart abstraction, not routinely available from HIV surveillance), at study enrollment, and then every 3 months up to and including month 12
- VL (via chart abstraction, not routinely available from HIV surveillance), at study enrollment, and then every 3 months up to and including month 12

CD4 cell counts and HIV RNA levels obtained from month 0 through month 12, will be extracted from participant's medical records to enable individual-level subgroup analyses of adherence and virologic responses among CARE+ participants who are receiving versus not receiving FIs for virologic suppression, as well as other subgroup analyses, such as:

- Behaviors likely to transmit HIV (sexual and parenteral)
- Receipt of and experience with services to promote retention and adherence
- Knowledge of, attitudes towards, and the feasibility of early initiation of ART
- Knowledge of and attitudes towards use of ART for prevention in partners

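### The month 0 patient survey follows the first randomised CARE+ session, so in the intervention arm the pooled baseline in Protocol 6.8 is a post-counselling measure and is at risk of bias

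*Protocol*

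**What the plan says.** Four sections of the protocol time the patient survey.

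- Section 6.2 (design): participants "will complete a patient survey module prior to and at the end of that study component".
- Section 6.5 (procedures): "At the end of the first (baseline, month 0) session, both arms will be presented, via the computer tool, with a series of questions".
- Section 6.7 (duration): patients "complete the survey upon enrollment in the Prevention for Positives study and at the end of that study component". The order within the enrolment visit is not given.
- Section 6.8 (analysis): "Patient surveys will be administered electronically, after the CARE+ intervention at the beginning and at the end of the intervention".

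On randomisation, section 6.5 says that assignment "is done automatically within the software application following the user's login with an anonymous study ID". On content, section 5.5 says that the full session, besides assessing self-efficacy and motivation, "provides tailored feedback on specific risk behaviors, shows skill-building videos, and helps the user make a risk-reduction plan". For controls, the Schema says that "participants in the control arm will only be administered behavior assessments via CARE+/ACASI and will not receive prevention messaging". On the survey itself, the Schema says: "The survey will assess their knowledge and attitudes towards ART use for treatment and prevention, ART adherence and FIs".

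Section 6.8 gives one aim for patients, a description of baseline knowledge, attitudes and practices on ART and related factors. The analysis is descriptive, by site and combined. No split by arm is mentioned.

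**The concern.** A baseline is meant to describe people before the randomised intervention reaches them. Under sections 6.5 and 6.8 that is true of the control arm only. The intervention arm answers after its first counselling session, and the two arms are then summarised together under the baseline label.

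What is at stake is the description that section 6.1 sets as an objective: what patients in care know and think about starting ART, about starting it at higher CD4 counts, about ART to prevent transmission, and about financial incentives. If the first session influences any of these answers, the pooled figure describes neither an uncounselled nor a counselled population. A pre-counselling value for the intervention arm cannot be recovered later by analysis, because it would never have been collected.

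**Working it through.** The protocol gives no sample size, effect or power figure for the patient survey, so there is no stated number to reproduce. The check is one of sequence, followed by simple arithmetic on an assumed shift.

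**Sequence at month 0, as sections 6.5 and 6.8 fix it**

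1. Login and automatic randomisation (6.5).
2. First session. Intervention: risk assessment plus counselling (5.5, 6.5). Control: risk assessment only (Schema, 5.5).
3. Patient survey in both arms (6.5, 6.8).

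Step 3 comes after randomisation in both arms and after counselling in one. Section 6.2 puts the survey ahead of the component, which cannot be squared with this order. Section 6.7 and the visit schedule in Appendix I place both activities at the enrolment visit and do not settle the order.

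**Share affected**

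Section 5.9.2 plans 660 per arm and 1,320 in total: 660 / 1,320 = 0.5.

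**Effect on the pooled baseline**

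Let *d* be the immediate shift, in percentage points, that the first session causes in a survey item in the intervention arm. The documents give no value for *d*, so a range including zero is assumed.

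- Error in the pooled baseline = 0.5 × *d*.
- Error in an intervention-arm change from month 0 to month 12, or in a between-arm difference in change, has size *d*, since the starting value is displaced by the full shift.

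| Assumed *d* (points) | Error in pooled baseline | Error in intervention-arm change, if one were computed |
|---|---|---|
| 0 | 0 | 0 |
| 5 | 2.5 | 5 |
| 10 | 5 | 10 |
| 15 | 7.5 | 15 |

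For the by-site summaries, the factor 0.5 is replaced by that site's own fraction in the intervention arm. Section 5.9.2 names gender as a possible stratum and does not name site, so that fraction may vary from site to site.

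**What is not touched**

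- The primary Prevention for Positives endpoint (5.9.1) is self-reported sexual behaviour and not a survey item on ART or incentives.
- A comparison of the arms at month 12 alone does not use the month 0 survey.
- The control arm's first survey follows no prevention messages, so it remains usable as an uncounselled baseline.

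**The case against.** The strongest reply is that the session and the survey cover different ground. CARE+ is described as counselling on sexual and behavioural risk. The survey asks about ART, adherence and incentives, along with sociodemographic facts and use of support services. Nothing in the protocol says that the session teaches about early ART or incentives, and one session cannot alter a past fact. This stands to a large extent: carry-over may be zero for many items. It does not dispose of the point, because the survey also covers ART as a means of preventing transmission, which lies close to the subject of the counselling. Carry-over there is plausible, though unmeasured.

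A second reply is that a descriptive survey may have been placed last on purpose, so that it does not prime or tire respondents before the behavioural risk questions. That is a fair reason for keeping it after the risk assessment. It is not a reason for keeping it after the counselling.

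A third is that the wording in section 6.2 is loose summary language beside the specific procedure in 6.5. That may explain the mismatch, but the specific procedure is the one that yields a post-counselling baseline.

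A reader might infer more: that the survey's change results are biased, with change understated in the intervention arm. The documents do not support that. Section 6.8 states no change analysis and no arm comparison for patients; its chi-squared comparison of baseline with study end sits under the provider aim. Because the module is repeated at month 12, a before-and-after reading is foreseeable, but it is not in this plan.

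**Conclusion.** The point holds as a risk of bias in one stated analysis, together with an internal contradiction on timing. The sequence is certain from the text: about half of the respondents give their baseline answers after randomised counselling. The bias is not shown. Its size depends on *d*, which the documents do not give. Over an assumed range of 0 to 15 points, the combined baseline would be off by 0 to 7.5 points, assuming equal allocation and similar survey completion in both arms. Any intervention-arm change from month 0 that was computed later would be off by the full *d*. The consequence is confined to the patient survey, and the randomised effectiveness comparison is not weakened.

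**What to change.** Reconcile sections 6.2, 6.5, 6.7 and 6.8 so that they state one order for month 0: login and randomisation, the ACASI risk assessment shared by both arms, the patient survey, and then, in the intervention arm only, the counselling content. Keeping the risk assessment first protects the behavioural baseline from priming by the survey. Items that ask about CARE+ itself may stay at the end of the session.

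If the present order is kept, section 6.8 should report month 0 survey results by arm, stop calling the intervention-arm values baseline, and use only the control-arm values as the uncounselled baseline. This needs no change to the software, but it leaves about half as many respondents for the baseline description.

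The cost of the preferred fix is a minor reordering of software modules before launch. No questions or visits are added. The intervention arm would take the survey before its counselling, which may cost some attention at that point.

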4.4 Study Sites for Viral Suppression

Twenty HIV care sites will be selected from Washington, D.C. and 20 HIV care sites will be selected from the Bronx to participate in this component of the study. Sites will be selected based on two primary criteria: 1) site agreement to participate in this component of the study, and 2) sites with the highest number of HIV-positive patients in care in the previous year. Additional site selection criteria may be considered if a total of 40 HIV care sites cannot be chosen based on the primary criteria.

HIV care sites will be randomized 1:1 to the FI vs. SOC, stratified by city and balanced by size of patient population in a clinic and baseline levels of proportion of VL showing suppression. In each city, these 20 sites will be randomized such that 10 will use the FI intervention, described in Section 4.5, to promote viral suppression in HIV-patients on ART and 10 will continue the existing SOC.

The site randomization will be balanced by the following two baseline characteristics:

• The size of the site's HIV-positive patient case load

• The proportion of HIV-positive patients with VL suppression at each site

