Prevention for Positives. In this component of the study, a subset of patients enrolled at select HIV care sites in the two intervention communities will be randomized either to an intervention arm (receiving computer-delivered intervention for sexual risk reduction plus SOC prevention activities) or to the control arm (receiving only the SOC prevention activities at the care site). Individual-level data will be collected and analyzed. This component is public health research requiring informed consent. Written informed consent will be obtained from participants.

Patient survey. All patients participating in the Prevention for Positives study component will be administered the Patient Survey. Individual-level data will be analyzed. This component is public health research. Written informed consent will be obtained from

participants at the time of consenting for participation in the Prevention for Positives study component.

Provider survey. Providers from participating HIV care sites will be invited to complete a Web-based survey regarding their knowledge, attitudes and practices concerning ART for treatment, frequency of HIV testing, and limited sociodemographic information. The survey will be anonymous, and will collect no identifying information. This component is public health research. Informed consent will be obtained from the provider's completing the survey. Before the survey will display, providers will read the consent and if they agree to participate, will indicate their agreement by clicking a button labeled "I agree." Investigator's Records

Study-specific records will only be located at HIV care sites participating in the Prevention for Positives study component. At these sites, all study source documents (such as informed consent forms and patient ID linkage logs) will be maintained in a locked cabinet or room. Access to these records will be restricted to appropriate study staff members, NIAID, OHRP, government or regulatory authorities, and/or IRB.

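### Section 6.8 compares the two provider-survey waves with a chi-squared test that ignores shared clinics and possible repeat responders, so its error rate is not controlled

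*Protocol*

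**What the plan says.** The Protocol's Schema sets the frame: "Providers at all participating HIV care sites will be invited to complete the provider survey". Section 4.4 gives the number of sites: "Twenty HIV care sites will be selected from Washington, D.C. and 20 HIV care sites will be selected from the Bronx". Section 6.2 has clinical providers surveyed "prior to and following the viral suppression intervention to assess trends in the provider knowledge, attitudes and practices". Section 6.7 sets the timing: "The provider survey will also take place twice, once at the time of initiation of the overall HPTN 065 study", with the second wave at the end of the viral suppression component.

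Recruitment under Section 6.6 is by letter, e-mail and telephone, "asking them to take the brief survey on a secure, anonymous website". Section 8.5 adds: "The survey will be anonymous, and will collect no identifying information".

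Section 6.8 summarises provider knowledge, attitudes and practices "at study baseline and study end by site and combined", and then names the test: "Chi-squared statistics will be used to compare the baseline data with study end data". It does not mention clinic or repeat response. Sections 3.8.4 and 4.8.4 leave their secondary analyses to the statistical analysis plan; Section 6.8 makes no such deferral.

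**The concern.** The comparison is before versus after within one pool of clinics. A two-sample chi-squared test assumes that responses are independent within each wave and between waves. Neither assumption is safe here:

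- Colleagues in one clinic share policies, training and patients, so their answers are likely to be correlated within a wave.
- Some providers will probably answer both times, and their two answers are likely to be positively correlated.

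These features push the standard error in opposite directions. Repeat responders and stable clinic effects make the true standard error smaller than the test assumes. Clinic effects that change between waves make it larger. Such changes are plausible: Section 4.4 randomizes half of the care sites in each city to financial incentives, and Section 6.1 lists attitudes towards those incentives among the survey objectives.

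At stake is whether a reported change in provider attitudes can be read at its stated significance level. The protocol models the dependence in its other comparisons: GEE with within-site correlation for linkage (Section 3.8.4.1), within-person and within-clinic correlation for viral suppression (4.8.4.1), and repeated-measures GEE for Prevention for Positives (5.9.4).

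**Working it through.** **No figure to reproduce.** The protocol states no sample size, effect, significance level or power for the provider survey. From the documents come two waves, 40 care sites, anonymity, and the site being known for by-site summaries. Everything else below is assumed, including a two-sided 5% level.

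**Formula under no change.** Let *m* be providers per clinic per wave, *f* the share answering both waves, *ρ* the correlation between one provider's two answers, and ICC_w and ICC_b the correlations between different providers in a clinic within a wave and between waves. Then:

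true variance / chi-squared variance, R = 1 + (m − 1)·ICC_w − [f·ρ + (m − f)·ICC_b]

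true size = 2·[1 − Φ(1.96/√R)]

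| m | ICC_w | ICC_b | f | ρ | R | True size |
|---|---|---|---|---|---|---|
| 5 | 0.05 | 0.05 | 1 | 0.6 | 1.20 − [0.60 + 0.20] = 0.40 | 0.002 |
| 5 | 0.05 | 0.05 | 0.8 | 0.4 | 1.20 − [0.32 + 0.21] = 0.67 | 0.017 |
| 5 | 0.05 | 0.05 | 0.5 | 0.4 | 1.20 − [0.20 + 0.225] = 0.775 | 0.026 |
| 10 | 0.05 | 0.025 | 0.5 | 0.4 | 1.45 − [0.20 + 0.2375] = 1.01 | 0.051 |
| 10 | 0.10 | 0.05 | 0.5 | 0.4 | 1.90 − [0.20 + 0.475] = 1.225 | 0.077 |
| 5 | 0.10 | 0 | 0 | – | 1.40 − 0 = 1.40 | 0.098 |
| 10 | 0.10 | 0 | 0 | – | 1.90 − 0 = 1.90 | 0.155 |

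The first and last rows are the extremes of the values tried. With no overlap and a fully stable clinic effect (ICC_w = ICC_b = 0.05), R = 1 − 0.05 = 0.95 and the size is 0.044. Shared clinics alone therefore do little harm; the inflation comes from clinic effects that shift between waves.

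**Power when repeat responders dominate.** Assume 200 responses per wave, a change from 50% to 60%, and no clinic effect. For f = 0.5 and ρ = 0.4:

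- R = [0.25 + 0.24 − 2·0.5·0.4·√(0.25·0.24)]/0.49 = (0.49 − 0.098)/0.49 = 0.80.
- True standard error = √(0.49/200)·√0.80 = 0.0495·0.894 = 0.0443.
- Pooled chi-squared standard error = √(2·0.55·0.45/200) = 0.0497.
- Chi-squared power = Φ[(0.10 − 1.96·0.0497)/0.0443] ≈ 0.52.
- Power using the true standard error = Φ(0.10/0.0443 − 1.96) ≈ 0.62.

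With f = 0.8, the power using the true standard error is 0.69 at ρ = 0.4 and 0.80 at ρ = 0.6. Chi-squared power stays at 0.52 to 0.53.

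**Does clustering by site work without a provider identifier?** Yes. A provider who stays at a clinic contributes both answers to the same site cluster, so a robust variance by site captures their covariance. In a simulation with 40 sites, about 240 providers per wave and 4,000 runs per scenario (power for 50% to 60%):

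| Scenario (assumed) | Size, chi-squared | Size, site-clustered | Power, chi-squared vs clustered |
|---|---|---|---|
| Full overlap, latent within-provider correlation 0.5 | 0.012 | 0.050 | 62% vs 76% |
| 60% overlap | 0.022 | 0.048 | 62% vs 71% |
| 30% overlap, clinic-by-wave shifts | 0.074 | 0.049 | – |
| 10% overlap, larger shifts | 0.112 | 0.054 | – |

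A second simulation, also with 40 sites and roughly 6 providers per site, gave 0.014 to 0.105 for chi-squared and 0.045 to 0.058 for the clustered test.

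**The case against.** A reader might infer that the same providers are surveyed twice, so that the test is simply too conservative and real changes will be missed. The documents do not support this. They describe two anonymous, voluntary waves, with no provider panel, retention plan or linkage. Overlap is likely because both waves recruit from the same sites, but its extent is not given. Nor is the direction fixed: plausible inputs give a conservative, an anti-conservative or an almost exact test.

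It can also be said that chi-squared statistics are a family that includes cluster-adjusted versions, and that such detail belongs in the statistical analysis plan. This has some force, but Section 6.8 names the method without qualification or deferral, while the protocol's other comparisons state their correlation structure. The ordinary reading is an unadjusted test.

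The low stakes are a fair point and stand. The design overview lists the surveys apart from the feasibility and effectiveness outcomes, the analysis is mainly descriptive, and no hypothesis, significance level or power is set.

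Finally, anonymity rules out pairing a provider's two answers as the survey is written. That excludes a McNemar-type analysis, but clustering by site does not need individual linkage.

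**Conclusion.** The point holds in limited form. The test named in Section 6.8 does not match a design in which both waves come from the same clinics and an unknown share of the same people. Its true size at a nominal 5% runs from about 1% to about 10% in the simulations, and from 0.2% to 15.5% at the extremes of the formula. In middle cases it is near nominal. These figures rest on assumed overlap, correlations and providers per clinic, none of which the protocol gives.

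The figure of 40 sites follows the Schema and Section 4.4. Section 6.3 speaks of select care sites, so there could be fewer, which would make a small-sample correction more important. Importance is minor: one secondary survey comparison is affected and no effectiveness conclusion depends on it.

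**What to change.** In Section 6.8, replace the chi-squared comparison for providers with a logistic GEE that has wave as covariate and HIV care site as the cluster, with small-sample-corrected robust standard errors. An equivalent site-clustered comparison would also serve, for example a Rao–Scott adjusted chi-squared test with the care site as cluster. Add a sentence that overlap of respondents between the waves is unknown and that individual answers are not linked.

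The cost is a change of wording and slightly more analysis work. The care site must be stored with each response, which the by-site summaries already require, so nothing further is collected and anonymity stays as it is. With little overlap there will be little or no gain in power. Where clinics shift differently between waves, the corrected test will reject less often than the chi-squared test, because its error rate is then controlled.
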